9.3.5. Intra-operative coagulation and blood loss monitoring in the operating room*

Coagulation prevention details, dose of heparin, either fixed or by titration, before and during surgery;

Monitoring of anti-coagulation, ACT, kaolin or celite;

The minimum operative ACT when available;

The estimated intra-operative blood loss, if available;

9.3.6. Transfusion (intra-operative and post-operative)*

Number of units of blood products transfused (red blood cells, platelets, fresh frozen plasma, cryoprecipitate, prothrombin complex concentrate, fibrinogen), if any.

9.3.7. Post-operative*

Reoperation if required with reason for re-operation;

The occurrence of post-operative stroke, post-operative myocardial infarction, other post-operative embolic or thrombotic event, and new post-operative dialysis and relative date;

Post-operative serum creatinine level;

Time to recover renal function baseline value, if available;

Any post-operative use of an aminoglycoside antibiotic;

The occurrence of multisystem failure;

Post-operative blood loss;

Status at discharge and if dead the primary cause of death before discharge;

Date of discharge (and post-operative stay).

Note: the average time-to-events for the abovementioned post-operative events are considered the following: less than one day for reoperation for bleeding (Karthik 2004), one day for renal failure (Rosner 2006), 3 days for stroke (Schwann 2007, Hogue 1999, Dafer 2006), 3 days for myocardial infarction (Thygesen 2007), and 6 days for deep vein thrombosis (Hogue 2006). All abovementioned post-operative events have to be collected at any time, even if those occur after the average time-to-events as published in the literature.

The non-key pages are the following:

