8.2. Primary objectives

The primary objectives of the Registry are to:

1. Monitor the pattern of use and record utilisation information:
 - the proportion of patients exposed to aprotinin in accordance with the authorized indication
2. Measure the incidence of the following adverse events:
 - death and the distribution of the primary cause of death
 - thromboembolic events; the total and individual incidence of myocardial infarction, stroke and other thromboembolic events recorded
 - incidence of renal dysfunction defined as a rise in creatinine from pre-operative to post-operative levels of > 0.5 mg/L, and the incidence of renal dialysis
 - the numbers having an anaphylactic response to aprotinin
3. Measure the effectiveness of risk minimisation measures as described in the RMP and close monitoring of adherence to the SmPC recommendations:
 - the proportion of patients receiving heparinisation monitoring as recommended in the SmPC
 - Proportion of patients with a minimal ACT-celite below 750 seconds
 - Proportion of patients with a minimal ACT-kaolin below 480 seconds
 - the proportion of patients with a post-operative renal dysfunction defined as a rise in creatinine from pre-operative to post-operative levels of > 0.5 mg/L or requiring dialysis known to have received aminoglycoside antibiotics
 - the proportion of patients exposed to aprotinin without the use of test dose (or antibody test)
 - the proportion of patients administered with the recommended posology
 - the proportion of patients administered with less than 2.5 million KIU
 - the proportion of patients administered with more than 7 million KIU

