9.7. Data analysis

All data analyses will be performed by Dendrite Clinical Systems together with Nordic after the Key Data are completed. Statistical programming and analyses will be performed using SAS and/or other statistical software as required.

Analysed data will be reviewed by an Independent Data Safety Monitoring Committee, involving at least four (4) national coordinating investigators.

The Registry will collect information for all patients who receive Nordic Aprotinin for any purpose in participating countries in Europe. The Registry will not allow a direct comparison of mortality and morbidity among patients treated with aprotinin to patients not with aprotinin. Mortality and morbidity outcomes vary according to patient selection criteria by centre and by country of treatment. Historical controls are not wholly reliable as patient selection and operative techniques vary over time. It is proposed to examine external data bases for comparative purposes as these may be used as a yardstick to measure patient outcomes, e.g. reports from existing national or European cardiac surgical databases. These external data will be mentioned in the Statistical Analysis Plan (SAP) prior to the first analysis.

The analysis of data from the Registry will be descriptive, and all information will be reported in summary tables.

The intention is to focus on those variables most pertinent to assessing compliance with approved labelling, including compliance with the approved indication, and compliance with instructions for appropriate use, including use of heparin and monitoring of anticoagulation. Summary data will be provided for all variables collected and the data will be reported overall, by country, and if required by centre.

The first data analyses will be conducted six months after the completion of data entry of the first subject in the study depending on PSUR scheme and timelines and will be repeated six months later. Thereafter the analyses will be conducted annually until the close of the Registry (i.e. for at least three years). Overall reports will be synchronised between each country so that **the analyses are all conducted at the same time.**

Analysis will be made of the data for Nordic Aprotinin overall, by individual country and if required by individual site. The analysis will include the following key outcomes and variables will be presented:

The outcomes to be included in each report will include at least:

- Death

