- Myocardial infarction (fatal and non-fatal)
- Renal failure (fatal and non-fatal)
- Renal failure with and without aminoglycoside use

- Stroke (fatal and non-fatal)
- Other embolic or thrombotic event (fatal and non-fatal)
- Blood loss: requiring blood product transfusion, requiring re-operation
- Blood product transfusion
- Anaphylaxis

Note: allergic reactions and anaphylactic/anaphylactoid reactions are rare (between 1/10,000 and 1/1,000) and anaphylactic shocks are very rare (below 1/10,000) when appropriate preventative measures are taken so none may be reported. If any occur the details will be reported separately.

Variables included in the analysis:

Analysis of each outcome will be presented by: country, age categories, sex, presence of anti-platelet agents active at time of operation, cardiac by-pass and operative type (on label and off-label). Other variables may be included as considered appropriate by an Independent Data Safety Monitoring Committee or as requested by the PRAC.

The final analysis will be based on the population entered at three years following completion of the first patient. The analysis will include at least the information above and will include further analyses as suggested by the results and as requested by the Competent Authorities concerned and the Independent Data Safety Monitoring Committee (IDSMC).

A review will be conducted by the IDSMC every six months throughout the study. The results of the six months initial interim report and of each annual report will be available in full to the PRAC to allow full review for safety signals. Previous mortality and morbidity data from existing cardiac surgery databases will be available as a yardstick. This may occur when a potential safety signal arises. Outcome data between different participating centres within the Registry may also be analysed when appropriate.

Additional analyses can be made available on a flexible basis depending on the outcomes in the study. In addition to the above further analyses may be undertaken when appropriate according to the ongoing findings from the Registry and as requested by the PRAC (and other Competent Authorities if required).

Rates and confidence intervals:

Rates and exact 95% confidence intervals will be computed for all identified adverse events and potential risks and all relevant criteria.

Missing data:

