As a matter of fact imputation of data is more or less invention of data that can strongly bias results in an observational study. The less speculative approach is therefore to remove from the data patients without the needed information from the analysis.

In data modelling or if a breakdown of the sample is done according a given variable, a missing data in any qualitative covariate (or factor of segmentation of the sample) can have a category called "unknown". A first model will fitted with such a categorization and a second one will be fitted after removing all patients with missing data on the covariate. If it concerns a breakdown of the sample then descriptive statistics along with 95% confidence interval will be provided for all categories including the unknown class. Regarding quantitative covariate, categorization of the covariate may be done and a first model will be fitted with only categorical variables including the "unknown" category and a

second model is fitted with quantitative covariate (patients with a missing data are excluded). Concerning the breakdown the same categorization approach will be applied and estimation will be provided for each category. If a breakdown of the sample is applied the estimation for the "unknown" category will be compared to all the other categories combined to assess whether missing data represent approximately the average of the collected data.

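### Under the 9.7 deletion rule, any summary of time to renal recovery covers only patients with a recorded recovery and would make recovery look faster than it is (minor)

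*Protocol*

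**What the plan says.** Three statements in the protocol bear on this.

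- Section 9.3.7, a Key Page, lists "Time to recover renal function baseline value, if available". It gives no recovery criterion, time origin, end of observation or entry for a patient who has not recovered. The same page collects "Status at discharge and if dead the primary cause of death before discharge" and the date of discharge.
- Section 9.7 states that "Summary data will be provided for all variables collected", overall, by country and, if required, by centre. It describes the method only in general terms: "The analysis of data from the Registry will be descriptive, and all information will be reported in summary tables".
- The missing-data paragraph of 9.7 rejects imputation and concludes: "The less speculative approach is therefore to remove from the data patients without the needed information from the analysis". The unknown category it offers is for covariates and factors used to split the sample, not for an outcome time.

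The renal objective in 8.2 is a different quantity: "incidence of renal dysfunction defined as a rise in creatinine from pre-operative to post-operative levels of > 0.5 mg/L, and the incidence of renal dialysis". Recovery time is in neither the primary nor the secondary objectives, nor in 9.7's minimum list of reported outcomes. Post-discharge follow-up (9.3.8) is non-key, collected where available, and lists renal failure but not recovery time.

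**The concern.** For most registry fields a blank means that nobody entered the value. Here a blank can itself be the outcome: the patient had not recovered when last seen, or died first. Removing such patients changes the question from how long renal dysfunction lasts in exposed patients to how quickly those with a recorded recovery recovered.

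Renal impairment is an important identified risk in the protocol's summary of safety concerns (Table 1), and this is the only listed variable that describes how long dysfunction takes to resolve. A reader of a bare median could take it as reassurance about reversibility, although the patients with the worst course contributed nothing to it.

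**Working it through.** **The plan's own figures.** The protocol states no figure for recovery time. Its sample-size figure reproduces: 1.96 × √(0.25/3,951) = 1.559%, and 3,951/0.75 = 5,268. That calculation concerns proportions and has no bearing here.

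**What the rules do to each type of patient with renal dysfunction**

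| Course | Recovery-time field | Under the 9.7 rule |
|---|---|---|
| Recovered, time entered | Value | Kept |
| Died unrecovered | No value can exist | Removed |
| Discharged alive unrecovered | Blank unless completed later | Probably removed |
| Recovered, time not entered | Blank | Removed |

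The second row follows from the meaning of the variable. The third is an inference: 9.3.7 does not say that recording stops at discharge, but the post-discharge page has no field for recovery time.

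**Illustration of size.** All inputs are assumptions. Let recovery time be exponential with true median m days, and let observation end at day L.

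- Rate: λ = ln 2 / m
- Share recovered by day L: F = 1 − exp(−λL)
- Median among those recovered: −ln(1 − F/2) / λ

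For m = 7 and L = 10: λ = 0.0990 and F = 1 − exp(−0.990) = 0.63. The median among recovered patients is −ln(1 − 0.314)/0.0990 = 3.8 days, which is 46% below 7.

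| True median (days) | L (days) | Median among recovered (days) | Shortfall |
|---|---|---|---|
| 4 | 8 to 14 | 2.7 to 3.5 | 32% to 12% |
| 7 | 8 to 14 | 3.2 to 4.7 | 54% to 32% |
| 14 | 8 to 14 | 3.6 to 5.8 | 74% to 58% |
| 3 | 7 to 14 | 2.2 to 2.8 | 26% to 6% |
| 5 | 7 to 14 | 2.7 to 4.0 | 46% to 19% |
| 10 | 7 to 14 | 3.1 to 5.4 | 69% to 46% |

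Every cell is short. The full span is about 6% to 74%.

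**Patients who never recover.** Let a fraction q never recover, with m = 5 among the rest and L = 10. The share with recovery by day 10 is (1 − q) × 0.75. The day by which half of all affected patients have recovered is −ln(1 − 0.5/(1 − q)) / λ.

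| q | Recovered by day 10 | Median among recovered (days) | Half of all affected recovered by day |
|---|---|---|---|
| 10% | 67.5% | 3.4 | 5.8 |
| 20% | 60% | 3.4 | 7.1 |
| 40% | 45% | 3.4 | 12.9 |

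The median among recovered patients does not move as lasting harm increases. The share recovered does, which is why the counts matter more than the median.

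**The case against.** The protocol never commits to a mean or median among recovered patients. The only link to an analysis is the general promise to summarise every variable. How to tabulate a minor descriptor is ordinarily settled in the SAP, which exists as Annex 6 but is not shown. Failure to recover, or death, might also be read as a not-applicable state rather than missing information. Section 9.9 promises to count missing values for each variable of key interest, and this might expose the shortfall.

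Much of this stands, and it limits the point to a conditional one. It does not remove it: the protocol's only written rule for an absent value is removal, with no exception for this field. A count of missing values does not by itself separate unrecovered, dead and unrecorded patients. Section 9.9 mentions a breakdown by cause, but the reasons given in section 5 say the database cannot hold explanations for missing data.

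A reader might infer three stronger things.

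- That recovery will look faster in the report. The documents do not support this, because no estimator is fixed and a properly labelled table would not mislead.
- That the worst renal outcomes are lost from the safety assessment. They are not: creatinine rise and dialysis are in the primary objective, and death and renal failure are in the minimum report list.
- That centre comparisons will be distorted by length of stay. Centre reporting is only if required, and no comparison of recovery times is planned.

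A fair objection also applies to the remedy. In a field completed only where available, a blank in a survivor may be an omission, and discharge may itself depend on renal recovery. Treating every blank as unrecovered should not be the sole analysis.

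**Conclusion.** The point holds as a conditional one. If recovery time is summarised under the removal rule of 9.7, the result is restricted to recorded recoveries and is biased towards fast recovery. The direction follows from the rule: a patient who dies unrecovered has no recovery time, and one discharged unrecovered has a time longer than the stay. The calculations assume a common end of observation, unrelated to the speed of recovery.

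The size cannot be established. The range of about 6% to 74% rests wholly on assumed medians, an exponential shape and a cut-off at discharge that the protocol does not state. The consequence is limited to one descriptive variable that supports no objective and no listed outcome. Priority: minor.

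**What to change.** In 9.7, exempt time to renal recovery from the removal rule. Take as denominator all patients who meet the 8.2 definition of renal dysfunction or need dialysis. Report numbers and proportions:

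1. with a recorded recovery;
2. discharged alive without a recorded recovery;
3. dead before recovery.

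Status and date at discharge are already Key Data, so these rows need no new field. Show any recovery time only beside these counts and labelled as among recovered patients.

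Optionally, add a cumulative incidence of recovery with death as a competing event and censoring at discharge. This needs a stated time origin and recovery criterion, which 9.3.7 lacks. Accompany it with a sensitivity row that treats blanks in survivors as unknown rather than unrecovered.

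The cost is a sentence in 9.7 and one extra table. The downside is that a blank in a survivor stays ambiguous, which is why the second row should say without recorded recovery rather than unrecovered.

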9.3.8. Post-discharge follow-up if available

Patient status follow-up (after discharge), whether alive or dead and if dead the primary cause of death;

Myocardial infarction, stroke and other embolic or thrombotic event;

Renal failure.

9.3.9. Cardiac history

Angina (Canadian Cardiovascular Society Angina Grading Scale Class I- IV)¹;

Dyspnoea (New York Heart Association)²;

¹ Angina (Canadian Cardiovascular Society Angina Grading Scale) Class I- IV.

- Class I: Angina only during strenuous or prolonged physical activity
- Class II: Slight limitation, with angina only during vigorous physical activity
- Class III: Symptoms with everyday living activities, i.e., moderate limitation
- Class IV: Inability to perform any activity without angina or angina at rest, i.e., severe limitation

² Dyspnoea. New York Heart Association Class I- IV

- Class I: Cardiac disease, but no symptoms and no limitation in ordinary physical activity, e.g. shortness of breath when walking, climbing stairs etc.
- Class II: Mild symptoms (mild shortness of breath and/or angina) and slight limitation during ordinary activity.

Previous myocardial infarctions within past 90 days;
Most recent myocardial infarction;
Congestive cardiac failure;

9.3.10. Previous interventions

Previous percutaneous coronary intervention and date of most recent intervention;
Previous operation requiring sternotomy;

9.3.11. Pre-operative risk factors

Height;
Weight;
Smoking history;
Diabetes treatment (diet, oral therapy and insulin);
Hypertension;
Hypercholesterolaemia;
Antiplatelet therapy;
Chronic lung disease;
Extracardiac arteriopathy;
Neurological dysfunction;
Poor mobility due to any non-cardiac reason;
Carotid bruits;
Pre-operative cardiac rhythm;
Active endocarditis;
Critical preoperative state;
Baseline figures of coagulation tests: activated partial thromboplastin time (aPTT), thrombin time (TT) and prothrombin time (PT)
Other relevant factors are derived from the Registry: the patient's age, body mass index, body surface area, and the duration of pre-operative and post-operative stay.

9.3.12. Pre-operative haemodynamic and circulation

Ejection fraction and value;
Pulmonary artery systolic pressure;
Catheterisation details;
Number of diseased coronary vessels;
Left main stem disease;

9.3.13. Pre-operative status and support

Use of intravenous nitrates;
Use of heparin or heparinoid of any kind;
Use of intravenous inotropes;
Patient ventilation;
The presence of cardiogenic shock;

9.3.14. Myocardial protection

Cardiopulmonary bypass;
The use of an intra-aortic balloon pump;
The use of a ventricular assisted device;
Time on bypass;
Extracorporeal membrane oxygenation.

-
- Class III: Marked limitation in activity due to symptoms, even during less-than-ordinary activity, e.g. walking short distances (20–100 m). Comfortable only at rest.
 - Class IV: Severe limitations. Experiences symptoms even while at rest. Mostly bedbound patients.

9.4. Data sources

The data source is an electronic registry that can be accessed worldwide through a web portal, working with all web browsers and designed to collect uniform data on patients exposed to Nordic Aprotinin. Data which is collected during routine clinical practice will be entered into the electronic case report form (eCRF). The Registry has been set up and implemented by Dendrite Clinical Systems on behalf of Nordic. The Registry has been tested by European experts in cardiac surgery and anaesthesiology.

9.5. Study size

All patients exposed to Nordic Aprotinin, at all participating cardiac surgical centres in European countries with marketing authorisation, are intended to be included during the study.

The study is designed primarily to monitor the pattern of use and record utilisation information such as the proportion of patients exposed to aprotinin in accordance with the authorized indication.

Considering that the registry of Great Britain & Ireland recorded just over 400,000 operations in 5 years and that the US one collected around 280,000 operations/year^{15,16}, we could postulate that, across Europe, at least 300,000 patients are undergoing cardiac surgery.

Thus, we estimate the sample size based on the occurrence of events of specific interest (such as type of procedure, death, thromboembolic, stroke ...) with a reasonable precision.

To obtain 95% confidence interval with a maximum margin error of 1.56%, 3,951 patients should be included. This margin error is the maximum one that can be obtained: it is the one based on the assumption that an event of interest is observed in 50% of patients (meaning a 95% CI of [48.44% ; 51.56%]). In all other cases (i.e. event of interest observed in less or more than 50%), precision will only be better (less than 1.56%).

There is no a priori calculation of power for this study because the main primary objective is descriptive rather than inferential and because the adverse event included in the other primary objectives such as in-hospital mortality, thromboembolic events or renal dysfunction are dependant of aprotinin's pattern of use.

Taking into account an exclusion rate of 25% (patient refusing data collection, un-exposed to aprotinin in the course of cardiac surgery with CPB, or undergoing off pump surgery), the number of patients to include is 5,268.

9.6. Data management

Data management and statistical analyses will be the responsibility of the Data Management and Statistics department at Nordic, Dendrite and CRO's site. The Investigators will register the patient data via an electronic web-based data collection system. Data collected during routine clinical practice will be entered into the electronic case report form (eCRF), by the Investigator, or associated site staff or a CRO. Quality control and data validation procedures will be applied to ensure the validity and accuracy of the database. The data capture software has been designed to allow for multi-layer data validation. Validation rules have been constructed so that invalid combinations of data are simply not permitted at the point of data entry. So, for example, if the end-user selected an answer of "No" to "Previous Cardiac Intervention" then all the other answers for type of procedure are greyed out including the date of previous procedure. Several logic checks have also been included. Window pops up in case Key Data are not entered.

Data collection will be by eCRF. Data will be available electronically to Nordic/CRO and an electronic copy supplied to the site.

A DHPC will be sent to cardiac surgery centres prior to launch in each participating countries in order to ensure that the information to healthcare professionals is up to date regarding aprotinin, notably the implementation of the Nordic Aprotinin Patient Registry, and the requirement to commit to enrol in the Registry to have access to Nordic Aprotinin. All participating sites will receive training in the study protocol requirements and data collection. When the end-user (Investigator or associated site staff) connects to the Registry, the end-user sees a table containing all concerned patients; when Key Data of a patient are complete, then the corresponding row is in green and when those data are incomplete the corresponding row is in yellow and reminds that “record is incomplete”. All participating sites will be monitored continually for completeness of data entry. When the Key Data, defined above, are not correctly completed, the site will be encouraged to improve compliance.

